3.2.2 Safety Variables

Safety endpoints include study drug exposure, adverse events, laboratory parameters, vital signs, electrocardiogram (ECG), ECOG performance status, concomitant medications, and physical examination.

Study Drug Exposure

Duration of treatment (i.e. exposure) for both tivozanib and sorafenib is defined as the time from the date of the first dose of study treatment to the date of the last dose of study treatment. Duration of treatment is calculated as: (last dose date – first dose date) + 1.

Adverse Event (AE)

Information regarding the occurrence of AEs will be collected throughout participation in this study, starting from the time the subject signs the informed consent form until a period of 30 days after the last dose of study drug. AEs will be coded by system organ class (SOC) and preferred term (PT) using the Medical Dictionary for Regulatory Activities (MedDRATM) Dictionary (Version 18.0 or later). Severity will be graded according to the National Cancer Institute (NCI) Common Terminology Criteria for Adverse Events (CTCAE) Version 4.03. AEs leading to death or study treatment discontinuation, treatment-related AEs, serious adverse events (SAEs), and treatmentemergent adverse events (TEAEs) will be considered with special attention.

A TEAE is defined as an AE (identified by PT) that begins or that worsens in severity after at least one dose of study treatment has been administered. That is, an AE is considered treatment-emergent if either of the following is met:

- The event begins on or after the first day of study treatment and before 30 days after the last dose of study treatment plus it was never recorded prior to the start of study treatment
- The event was recorded or began prior to the start of study treatment but increased in NCI CTCAE v4.03 grade on or after the first dose of study treatment

Laboratory Parameters

The following laboratory parameters will be collected in accordance with the schedule of assessments as specified in Table 1 of the study protocol:

- Hematology: complete blood count with differential and platelet count
- Serum Chemistry: sodium, potassium, chloride, bicarbonate (optional), blood urea nitrogen (BUN), creatinine, glucose, total bilirubin, direct bilirubin, aspartate aminotransferase (AST), alanine aminotransferase (ALT), lactase dehydrogenase (LDH), alkaline phosphatase, calcium, magnesium, phosphorus, albumin, amylase, lipase, and total protein
- Coagulation: prothrombin time (PT) and/or international normalized ratio (INR), and partial thromboplastin time (PTT)
- Thyroid Function: Free T4 (thyroxine), and thyroid stimulating hormone (TSH) levels. Total T3 (triiodothyronine) is optional
- Urinalysis: protein, glucose, ketones, urobilinogen, occult blood, microscopic sediment evaluation, and 24-hour urine test (required only when protein is at least 4+)
- Pregnancy: serum ß-human chorionic gonadotropin (hCG) for premenopausal, non-sterilized females

Vital Signs

Vital sign assessments will be collected in accordance with the schedule of assessments as specified in Table 1 of the study protocol after a subject has been sitting for 5 minutes. They will include measurements of diastolic and systolic blood pressure (mmHg), heart rate (beats per minute), respiration rate (breaths per minute), and body temperature (Celsius).

Electrocardiogram (ECG)

A 12-lead ECG will be performed in accordance with the schedule of assessments as specified in Table 1 of the study protocol after a subject has been supine for approximately 10 minutes. This assessment will include results categorized as normal; abnormal, not clinically significant; abnormal, clinically significant; or unevaluable.

ECOG Performance Status

In accordance with the schedule of assessments as specified in Table 1 of the study protocol, ECOG performance status will be recorded as follows:

- 0 = Fully active, able to carry on all pre disease performance without restriction.
- 1 = Restricted in physically strenuous activity but ambulatory and able to carry out work of a light or sedentary nature, e.g., light house work, office work.
- 2 = Ambulatory and capable of all self-care but unable to carry out any work activities. Up and about more than 50% of waking hours.
- 3 = Capable of only limited self-care, confined to bed or chair more than 50% of waking hours.
- 4 = Completely disabled. Cannot carry on any self-care. Totally confined to bed or chair.

5 = Death

Concomitant Medications

Any medication that a subject takes other than tivozanib or sorafenib during the duration of treatment is considered a concomitant medication. Information regarding the usage of concomitant medications will be collected throughout participation in this study, starting from the time the subject signs the informed consent form until a period of 30 days after the last dose of study drug. For each concomitant medication taken during the study, the generic component will be identified using the World Health Organization Drug (WHO Drug) Dictionary.

Physical Examination

A complete physical examination (PE) will be performed at screening by a physician or staff member who is qualified to perform such examinations. The complete PE will entail a thorough review of all body systems, including weight (kg) and height (cm). The remaining PE assessments will be directed PEs, but must include weight (kg). They will be done in a targeted manner, covering body systems related to the subject's disease or relevant findings in the complete PE.

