6 DIAGNOSIS AND MAIN CRITERIA

6.1 Subject Inclusion Criteria

Subjects may be male or female, and must meet all of the following inclusion criteria to be eligible for participation in the study.

1. \geq 18-years of age.

2. Subjects with metastatic RCC who have failed 2 or 3 prior systemic regimens, one of which includes a VEGFR TKI other than sorafenib or tivozanib.
 - a. Postoperative or adjuvant systemic therapy will not be counted as a prior therapy unless recurrence is detected within 6 months of completion of treatment, in which case it will be counted as a prior therapy for metastatic disease.
 - b. Subjects must be off all systemic anti-cancer therapy or radiotherapy for at least 2 weeks prior to Cycle 1 Day 1.
3. Subjects must have recovered from the AEs of prior therapy or returned to baseline. Controlled AEs such as hypothyroidism or hypertension are permitted.
4. Histologically or cytologically confirmed RCC with a clear cell component (subjects with pure papillary cell tumor or other non-clear cell histologies, including collecting duct, medullary, chromophobe, and unclassified RCC are excluded).
5. Measurable disease per the RECIST criteria (Version 1.1, see Appendix A).
6. ECOG performance status of 0 or 1.
7. Life expectancy \geq 3 months.
8. If female and of childbearing potential, documentation of negative pregnancy test prior to enrollment.
9. Ability to give written informed consent and comply with protocol requirements.
10. Sexually active pre-menopausal female subjects (and female partners of male subjects) must use adequate contraceptive measures, while on study and for at least 90 days after the last dose of study drug. Sexually active male subjects must use adequate contraceptive measures, while on study and for at least 90 days after the last dose of study drug. All fertile male and female subjects and their partners must agree to use a highly effective method of contraception. Effective birth control includes (a) IUD plus one barrier method; or (b) 2 barrier methods. Effective barrier methods are male or female condoms, diaphragms, and spermicides (creams or gels that contain a chemical to kill sperm). (Note: oral, implantable, or injectable contraceptives may be affected by cytochrome P450 interactions, and are not considered effective for female subjects in this study.)

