12.1.2 Medical History

Medical conditions present at the initial study visit are defined as medical history, and are NOT to be considered AEs. These medical conditions should be adequately documented on the medical history page of the eCRF. However, medical history conditions, other than the disease under study, that worsen in severity or frequency during the study and are considered clinically significant by the Investigator should be recorded and reported as AEs.

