4.8.2 Adverse Events

Adverse events will be coded by system organ class (SOC) and preferred term (PT) using the Medical Dictionary for Regulatory Activities (MedDRATM) Version 18.0 or later.

A TEAE is defined as an AE (identified by PT) that begins or that worsens in severity after at least one dose of study treatment has been administered. Treatment-related TEAEs are those with reasonable causality to study drug marked as "yes" on the eCRF. TEAEs with an outcome of death are those with a grade of 5 or an outcome of "fatal." TEAEs leading to treatment withdrawal are those with a study drug action taken of "drug withdrawn," while TEAEs leading to study drug dose reduction or interruption are those with a study drug action taken of "dose reduced" or "drug interruption" (respectively).

Summary tables will be presented for TEAEs by treatment arm. An overall presentation of TEAE information will include the following:

- Number and percentage of subjects with at least one TEAE
- Number and percentage of subjects with at least one TEAE of Grade 3 or higher
- Number and percentage of subjects with at least one treatment-related TEAE
- Number and percentage of subjects with at least one treatment-related TEAE of Grade 3 or higher
- Number and percentage of subjects with at least one serious TEAE

- Number and percentage of subjects with at least one treatment-related serious TEAE
- Number and percentage of subjects with at least one TEAE leading to death
- Number and percentage of subjects with at least one treatment-related TEAE leading to death
- Number and percentage of subjects with at least one TEAE leading to treatment withdrawal
- Number and percentage of subjects with at least one treatment-related TEAE leading to treatment withdrawal
- Number and percentage of subjects with at least one TEAE leading to dose reduction
- Number and percentage of subjects with at least one treatment-related TEAE leading to dose reduction
- Number and percentage of subjects with at least one TEAE leading to dose interruption
- Number and percentage of subjects with at least one treatment-related TEAE leading to dose interruption

TEAE information will also be presented by NCI CTCAE severity grade and by relationship to study treatment. If a subject had more than one occurrence of a TEAE, the most severe grade will be used in the summary tables.

The following summaries will be provided:

- Number and percentage of subjects for each TEAE, categorized by SOC and PT

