For missing or partially missing dates, imputation will be done according to Section 4.7.1.3. In general, however, adverse events will be assumed to be treatment-emergent unless there is clear evidence (through comparison of partial dates) to suggest that the adverse event started prior to the date of first dose of study treatment or more than 30 days after the date of last dose of study treatment.

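### The working TEAE rule in SAP 3.2.2 is narrower than its own lead sentence and SAP 4.8.2, and read literally it leaves same-grade or lower-grade recurrences out of the TEAE tables

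*SAP*

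**What the plan says.** SAP 3.2.2 starts with a broad definition ("A TEAE is defined as an AE (identified by PT) that begins or that worsens in severity after at least one dose of study"), which turns only on onset or worsening once dosing has begun. It then restates this as two criteria, either of which is enough.

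- Criterion 1: the event begins on or after the first treatment day and "before 30 days after the last dose of study treatment plus it was never recorded prior to the start of study treatment".
- Criterion 2: "The event was recorded or began prior to the start of study treatment but increased in NCI CTCAE v4.03 grade", with the increase falling after dosing starts. No reference grade is named, and no closing date is given.

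SAP 4.8.2, which governs the adverse event analysis, repeats only the broad sentence ("A TEAE is defined as an AE (identified by PT) that begins or that worsens in severity after at least one dose") without the two criteria. Its default for incomplete dates is that "adverse events will be assumed to be treatment-emergent unless there is clear evidence (through comparison of partial dates"; the evidence in question is when the event started, not whether the term had appeared before.

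On outputs, SAP 4.8.2 says "Summary tables will be presented for TEAEs by treatment arm". Protocol 12.1.2 separates history from events: "Medical conditions present at the initial study visit are defined as medical history, and are NOT to be considered AEs". It also asks that a history condition which becomes more severe or more frequent, and is judged clinically significant, be reported as an adverse event.

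**The concern.** The two criteria are introduced as an explanation of the lead sentence, but they change it. An event can begin after first dose, satisfy the lead sentence and 4.8.2, and still fail both criteria because the same preferred term was on record earlier at an equal or higher grade. Two programmers working from 3.2.2 and 4.8.2 could produce different adverse event tables from the same data. The sections also pull apart on dates: a recurrence with an incomplete date is presumed treatment-emergent, while the same recurrence with a full date can be excluded.

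Comparing safety and tolerability is a stated secondary objective, and the adverse event summaries that serve it are all built on the TEAE flag. The trial is open-label, so the choice of definition should not be left until event data by arm are being tabulated.

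**Working it through.** The plan attaches no figure to this rule, so there is none to reproduce. The check is a comparison of the rules, followed by arithmetic that shows direction only.

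**1. The rules as logic.**
- SAP 3.2.2 criteria: (onset in window AND term not on record before dosing) OR (term on record before dosing AND grade > reference grade).
- Lead sentence and SAP 4.8.2: onset after first dose OR severity rises.

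**2. Cases.** Every event is on treatment and inside the window. Grade 0 at first dose means the earlier episode had resolved.

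| Earlier recorded grade | Grade at first dose | On-treatment grade | 3.2.2, reference = earlier recorded grade | 3.2.2, reference = grade at first dose | Lead sentence / 4.8.2 |
|---|---|---|---|---|---|
| none | 0 | 1 or 3 | TEAE | TEAE | TEAE |
| 1 | 0 | 1 | not | TEAE | TEAE |
| 2 | 0 | 1 | not | TEAE | TEAE |
| 2 | 0 | 2 | not | TEAE | TEAE |
| 3 | 0 | 2 | not | TEAE | TEAE |
| 3 | 0 | 3 | not | TEAE | TEAE |
| 2 | 0 | 3 | TEAE | TEAE | TEAE |
| 1 | 1 | 2 | TEAE | TEAE | TEAE |
| 2 | 2 | 2 | not | not | not |

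The definitions disagree only on resolved events that recur at the same or a lower grade, and only if the grade is measured from the earlier record. A recurrent Grade 3 after an earlier Grade 3 is among them.

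**3. Which outputs use the flag.**
- Affected (SAP 4.8.2): the TEAE overview and the tables by system organ class and preferred term; the optional exposure-adjusted rates; and the listings of treatment-emergent SAEs and of TEAEs leading to withdrawal, reduction or interruption.
- Not affected: the listing of all adverse events (4.8.2), dose reductions and interruptions with reasons (4.8.1), laboratory grades and shifts (4.8.4), and vital signs with markedly abnormal blood pressure (4.8.5).

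**4. What counts as recorded.** The SAP does not say.
- AE records only: collection begins at consent (Protocol 12.5), so the reach is consent to first dose. That is usually the 21-day screening period, but consent may come earlier (Protocol 7.1) and re-screening is unlimited (5.4.1).
- Medical history included: Protocol 7.1 collects past as well as current conditions, every subject has failed two or three regimens with a VEGFR TKI among them, and "Controlled AEs such as hypothyroidism or hypertension are permitted" at entry. The rule would then reach toxicities of earlier therapy. The protocol lists no CTCAE grade among the history items, so criterion 2 may have nothing to compare.

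**5. Direction of the effect.** Let f be the share of subjects with the event whose event is dropped. With f equal in both arms, tabulated rate = r × (1 − f). The documents give no value for f; 10% and 50% are assumptions. The rates r come from the earlier Phase 3 trial (Protocol 3.6.2), tivozanib vs sorafenib.

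- Hypertension, 44.0% vs 34.2%: difference 9.8 points, ratio 44.0/34.2 = 1.29.
  - f = 10%: 44.0 × 0.9 = 39.6; 34.2 × 0.9 = 30.8; difference 8.8; ratio 1.29. With 161 per arm, 161 × 0.440 × 0.1 = 7.1 and 161 × 0.342 × 0.1 = 5.5 subjects dropped.
  - f = 50%: 22.0 vs 17.1; difference 4.9; ratio 1.29; 35.4 and 27.5 subjects dropped.
- Hand-foot syndrome, 13.1% vs 54.1%: difference 41.0 points. At f = 10% it is 41.0 × 0.9 = 36.9; at f = 50% it is 41.0 × 0.5 = 20.5. The ratio stays at 54.1/13.1 = 4.13.

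So equal loss shrinks absolute differences in whichever direction they run and leaves ratios alone.

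**The case against.** The strongest reply is that criterion 2 may be meant to measure from the subject's state at first dose. A resolved event then sits at grade 0, any recurrence is an increase, and nothing in the table is lost beyond what the lead sentence also leaves out. The SAP does not exclude this reading. It would, however, leave the never-recorded condition in criterion 1 with almost nothing to do, and the reference grade would still need to be written down.

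Second, a reader might infer that recurring toxicities disappear from all safety reporting. They do not. The outputs listed in step 3 as unaffected remain, and for hypertension the blood pressure tables are an independent source.

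Third, a reader might infer that toxicities of earlier TKI therapy are routinely removed. The documents do not establish this. Conditions present at the initial visit are not adverse events, preferred-term coding is described for adverse events but not for medical history, and entry requires earlier toxicities to have settled or returned to baseline. Whether the rule reaches that far depends on an undefined word.

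Fourth, severe events are partly protected. A fatal event exceeds any earlier recorded grade, and a Grade 3 or higher event is lost only if the same term was on record at that grade or above, or if an ungraded history entry counts as a record.

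Fifth, SAP 4.8.2 plans no between-arm test of adverse events, so no formal inference changes.

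These points limit the reach and size of the problem. They do not remove the disagreement between the two sections.

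**Conclusion.** The point holds in a limited form. As written, the criteria in SAP 3.2.2 exclude an on-treatment event whose preferred term was recorded before dosing at an equal or higher grade, contrary to their own lead sentence and to SAP 4.8.2. If medical history is a source of records, they also conflict with Protocol 12.1.2, because a history condition that becomes more frequent without a grade rise is reportable as an adverse event yet fails both criteria.

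The conclusion assumes that 3.2.2 is the version programmed and that the grade is compared with the earlier record. On those assumptions, the minimum reach is events recorded between consent and first dose.

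The size cannot be estimated. The percentages in step 5 are not an estimate and should not be read as a bound: f has no source, the earlier trial barred prior anti-angiogenic therapy, and its TEAE rule is not given. The unchanged ratio rests on f being equal in both arms. That need not be so, since whether a recurrence passes criterion 2 depends on its grade on treatment. Nor do the documents show that the rule favours one drug: equal loss would narrow the hypertension gap and the hand-foot syndrome gap alike. This should be corrected, but it does not undermine the safety evaluation as a whole.

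**What to change.** Use one definition, worded identically in SAP 3.2.2 and 4.8.2.

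- In criterion 1, delete everything in "before 30 days after the last dose of study treatment plus it was never recorded prior to the start of study treatment" from the word plus onward.
- Count an adverse event as treatment-emergent if its onset is on or after first dose and up to 30 days after last dose, whatever was recorded earlier under the same preferred term.
- Also count an event ongoing at first dose if it rises above its grade at first dose within that same window. This supplies the missing reference grade and closing date.
- Count a medical-history condition that is reported as an on-treatment adverse event under Protocol 12.1.2 as treatment-emergent. No history grade is then needed, and the meaning of recorded no longer matters.

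This is more than copying 4.8.2 into 3.2.2: the definition sentence in 4.8.2 has no time window, no reference grade and no rule for medical history.

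The cost is one SAP paragraph and one derivation flag. No study procedure or data collection changes. Reported adverse event rates will rise slightly in both arms.

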4 STATISTICAL METHODS

4.1 Data Quality Assurance

All tables, figures, and data listings to be included in the report will be independently checked for consistency, integrity and in accordance with standard PAREXEL procedures.

4.2 General Presentation Considerations

'Baseline' is defined as the last observation on or before Cycle 1 Day 1. Baseline assessments should occur within 7 days of Cycle 1 Day 1. 'End of Treatment' is defined as the last available observation up to 7 days after the last dose of study treatment. 'End of Study' is defined as the last available observation after 'End of Treatment'.

Durations are calculated as the stop date minus the start date plus one.

For elapsed time (e.g. time since the initial diagnosis) if the reference date is on or after the event date, then the elapsed time is the reference date minus the event date plus one. If the reference date is before the event date then the elapsed time is the reference date minus the event date.

Unscheduled assessments (laboratory data, ECG, or vital signs associated with nonprotocol clinical visits or obtained in the course of investigating or managing adverse events) will be included in listings, but not summaries. If more than one laboratory value is available for a given visit, the first valid observation will be used in summaries and all observations will be presented in listings. If it is not possible to determine which is the first measurement due to missing times then the average of all measurements for that time point will be used as the value for that time point.

Continuous data will be summarized in terms of the mean, standard deviation (SD), median, minimum, maximum, and number of observations, unless otherwise stated. Continuous data that are expected to be skewed will be presented in terms of the maximum, upper quartile, median, lower quartile, minimum, and number of observations. The minimum and maximum will be reported to the same number of decimal places as the raw data recorded in the database. The mean, median, lower quartile, and upper quartile will be reported to one more decimal place than the raw data recorded in the database. The SD will be reported to two more decimal places than the raw data recorded in the database. In general, the maximum number of decimal places reported shall be four for any summary statistic.

Categorical data will be summarized in terms of the number of subjects providing data at the relevant time point (n), frequency counts, and percentages. Any planned collapsing of categories will be detailed in the corresponding sections of this SAP and within the data displays. Percentages will be presented to one decimal place. Percentages will not be presented for zero counts. Percentages will be calculated using n as the denominator.

Changes from baseline in categorical data will be summarized using shift tables where appropriate.

P-values greater than or equal to 0.001, in general, will be presented to three decimal places. P-values less than 0.001 will be presented as "<0.001" and p-values greater than 0.999 will be presented as ">0.999".

Confidence intervals will be presented to one more decimal place than the raw data.

All report outputs will be produced using SAS[®] version 9.2 or a later version in a secure and validated environment. Each report output will be provided to the sponsor in a single Microsoft Word document.

